4.1 Schedules of Assessments (SoA)

Table 1: Schedule of Assessments (Part 1a)

	Screening		Treatment			Outpatient Visits (Cohorts 4 and 5 only)		Follow-Up ¹
	D-28 to -2	D-1	D1	D2	D3 (Discharge ² or early termination)	D4	D5	D8 (between Days 8 and 11)
Informed consent	X							
Height and BMI	X							
Weight	X	X			X			
Inclusion/Exclusion Criteria	X	X ³	X					
Demographics ⁴	X							
Medical History		X						
Concomitant Medications						Continuously		
Physical and Neurological Examination	X	X			X			X
Vital Signs including orthostatic vital signs, 12-lead ECG, Body Temperature ⁵	X	X	X	X	X			X
12-Lead Telemetry ⁶			X	X	X			
Hematology, Clinical Chemistry, HbA1c, and Urinalysis ⁷	X	X	X	X	X			X
Thyroid Panel	X	X			X			X
Coagulation Tests	X	X			X			
Drug Screening, Alcohol Breath, and Urine Cotinine Test	X	X						
COVID-19 PCR	X	X						
Virus Serology	X							
Study Drug Administration			X					
PK Blood Sampling ⁸			X	X	X	X	X	
PK Urine Sampling ⁹			X	X	X			
FSH Test in Post-Menopausal Participants ¹⁰	X							
Pregnancy Test ¹¹	X	X			X			
C-SSRS	X	X						X
Adverse Events						Continuously		
Outpatient Visits	X					X	X	X
Residence in Clinic				X				

D=day; ECG=electrocardiogram; PK=pharmacokinetic

1. Follow-up examination will take place on Day 8 (or between Day 8 and 11).
2. Discharge after completion of all study 48-hour assessments.
3. Continuous eligibility assessments on Day -1 including continuous medical history on Day -1 and prior to dosing on Day 1.
4. Including sex, date of birth, race, and ethnicity.
5. Will be performed at Screening, at admission on Day -1, Day 1 pre-dose (up to 60 min pre-dose), and 1 (± 20 min), 2 (± 20 min), 4 (± 20 min), 8 (± 60 min), 12 (± 60 min), and 16 (± 60 min) hours post-dose, at Day 2 (24 and 36 [± 60 min] hours post-dose), on Day 3 (48 [± 60 min] hours post-dose), and at Follow-up. Orthostatic vital signs will be measured at Screening and at admission on Day -1 only.
6. Will be started approximately 1-2 hours pre-dose at Day 1 and will be continued to approximately 48 hours post-dose.
7. Will take place at Screening (in fasted state, i.e., participants should fast for 4 hours prior to sample collection), at Day -1 (in fasted state), Day 1 at 8 hours post-dose (in not-fasted state), at Day 2 (in fasted state), at Day 3 (in fasted state), and at Follow-up (in fasted state). HbA1c will be performed at Screening.

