Vital Signs including orthostatic vital signs, 12-lead ECG, Body Temperature ⁵	X	X	X	X	X	X	X			X
12-Lead Telemetry ⁶			X	X		X	X			
Hematology, Clinical Chemistry, HbA1c, and Urinalysis ⁷	X	X	X	X	X		X			X
Thyroid Panel ⁸	X	X			X		X			X
Coagulation Tests	X	X					X			
Drug Screening, Alcohol Breath, and Urine Cotinine Test	X	X								
COVID-19 PCR	X	X								
Virus Serology	X									
Study Drug Administration			X	X	X	X				
PK Blood Sampling ⁹			X	X	X	X	X	X	X	
FSH Test in Post-Menopausal Participants ¹⁰	X									
Pregnancy Test ¹¹	X	X					X			
C-SSRS	X	X					X			
Adverse Events							Continuously			
Outpatient Visits	X							X	X	X
Residence in Clinic					X					

D=day; ECG=electrocardiogram; PK=pharmacokinetic

1. Follow-up examination will take place 7 days after the last dose, on Day 19 or between Day 19 and Day 22.
2. Discharge after completion of all study 36-hour post-Day 12 dose assessments.
3. Continuous eligibility assessments on Day -1 and Day 1 prior to dosing.
4. Including sex, date of birth, race, and ethnicity.
5. Will take place at Screening, at admission on Day -1, on Day 1 pre-dose (up to 60 minutes pre-dose) and 1 (± 20 min), 2 (± 20 min), 4 (± 20 min), 6 (± 60 min), 8 (± 60 min), 12 (± 60 min); on Days 2-11 on pre-dose (up to 60 minutes pre-dose) and 4 (± 20 min) hours post-dose; on Day 12, pre-dose (up to 60 minutes pre-dose) and 1 (± 20 min), 2 (± 20 min), 4 (± 20 min), and 8 (± 60 min) hours post-dose; on Day 13 (in the morning); and at Follow-up. Orthostatic vital signs will be measured at Screening and at admission on Day -1 only.
6. Will be started on Day 1 and Day 12: approximately 1-2 hours pre-dose and will be continued to approximately 24 hours post-dose.
7. Will be performed at Screening (in fasted state, i.e., participants should fast for 4 hours prior to sample collection), Day -1 (in fasted state), on Day 1 at 8 hours post-dose (in not fasted state) and on Days 2, 6, 13 (in fasted state), and Follow-up (in fasted state). HbA1c will be performed at Screening.
8. A thyroid panel (TSH, FT3, and FT4) will be performed at Screening, on Day -1, on Day 6, Day 13, and at the Follow-up Visit.
9. Will take place:
 - on Day 1: pre-dose (within 2 hours of dosing) and 0.25 (± 2 min), 0.5 (± 2 min), 1 (± 5 min), 1.5 (± 5 min), 2 (± 5 min), 3 (± 10 min), 4 (± 10 min), 6 (± 10 min), 8 (± 10 min), 12 (± 10 min), and 16 (± 30 min) hours post-Day 1 dose,
 - on Day 2: at 24 hours (± 30 min) and 36 hours (± 30 min) post-Day 1 dose,

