7.1.1 Part 1a (SAD)

After assessing eligibility during a 4-week screening period, approximately 40 healthy participants will participate in Part 1a. Each eligible participant will be assigned to 1 of 5 cohorts (8 participants per cohort) to evaluate a total of up to 5 single ascending dose levels. Proposed dose levels are:

Cohort 1: 5 mg

Cohort 2: 10 mg

Cohort 3: 20 mg

Cohort 4: 40 mg

Cohort 5: 80 mg

The starting dose will be 5 mg. Following completion of each ascending dose level, an SRC will review the safety and tolerability data through the follow-up visit of a minimum of 6 evaluable participants. The SRC will also review PK data for up to 48 hours post-dose in at least 6 evaluable participants in order to make decisions whether to escalate to the next planned dose level, decrease the next dose level, repeat a dose level, or to not evaluate any additional dose. The determination of the highest dose level for this study will be based on emerging safety/tolerability and PK data, as recommended by the SRC, but will not exceed the maximum dose currently outlined in the protocol.

For each dose level, 6 participants will receive ATH-399A and 2 participants will receive placebo. Each cohort will utilize sentinel dosing, with one participant receiving ATH-399A and one participant receiving placebo. Provided no clinically significant safety issues are noted in the 48 hours after dosing the initial 2 participants in the cohort, the 6 remaining participants in the cohort will be dosed. Before dosing the rest of the cohort, the Investigator will initiate a discussion via e-mail with the Sponsor's Medical Monitor (MM) or representative to review the available safety and tolerability data of the sentinel participants in order to make a decision regarding continuation of the study with the remaining 6 non-sentinel participants. In the case of

clinically significant safety issues or a sentinel stopping rule is present, then an ad hoc SRC meeting and/or a MM call can be necessary.

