Participants will be admitted to the clinical unit on the day before study drug administration (Day -1) for baseline assessments, and to confirm eligibility. Participants will be dosed in the fasted state and will be required to fast for a minimum of 10 hours prior to dosing and 4 hours following dosing. Except for water given with the study drug, no fluids will be allowed from 1 hour before dosing until 1 hour after dosing. Participants in Study Part 1a will stay in the clinical unit for 4 days (3 nights), from Day -1 until Day 3. Blood samples for PK analysis for Cohorts 1, 2, and 3 will be collected pre-dose and at specified time points up to Day 3 (48 hours) post-dose and blood samples for PK analysis for Cohorts 4 and 5 will be collected pre-dose and at specified time points up to Day 5 (96 hours) post-dose. Urine samples for PK analysis will be collected from pre-dose and during specified time intervals up to Day 3 (48 hours post-dose). PK blood samples for Cohorts 4 and 5 will be collected at outpatient visits on Day 4 (72 hours post-dose) and Day 5 (96 hours post-dose). All participants in each cohort will return for a follow-up visit on Day 8 (between Day 8 and Day 11).

Physical and neurological examinations, safety labs (including drug screen, cotinine test, and alcohol breath test), vital signs, ECG, and telemetry will be performed at specified time points. AEs will be recorded throughout the study. For details regarding the timing of specific procedures, see [Table 1](#).

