7.2 Justification for Dose

[REDACTED]

study progresses. The SRC recommendations should be based on results from a minimum of 6 evaluable participants in each dosing cohort.

Safety/tolerability data through the final follow-up visit for each of the 6 evaluable participants in a cohort along with PK data up to at least 48 hours post-dose in Part 1a and 1b (or 24 hours post-last dose in Part 2) will be assessed by the SRC prior to:

- a. Ascending from one dose-level cohort to the next higher dose level cohort in Parts 1a and 2,
- b. Prior to transitioning from Part 1a to Parts 1b and 2.

The SRC will stop dose escalation or descend to a dose level lower than the planned next higher dose level if any of the following criteria are met:

- One participant per cohort who receives ATH-399A experiences a serious adverse event (SAE) which is considered to be related to the study medication.
- Two participants per cohort who receive ATH-399A have QTc prolongation, defined as an average absolute (regardless of baseline value) QTcF >500 msec or an increase of QTcF > 60 msec above baseline, confirmed by repeating after 5 minutes, and determined post-dose.
- Two participants per cohort who receive ATH-399A exhibit hypotension, defined as resting supine diastolic blood pressure <40 mmHg persisting for at least 10 minutes on repeated assessment, or an asymptomatic or symptomatic fall in systolic blood pressure to below 80 mmHg, persisting for at least 10 minutes on repeated assessment.
- Two participants per cohort who receive ATH-399A exhibit hypertension, defined as an increase in resting systolic blood pressure to above 180 mmHg, persisting for at least 10 minutes, or an increase in resting diastolic blood pressure to above 105 mmHg, persisting for at least 10 minutes.
- Two participants per cohort who receive ATH-399A exhibit tachycardia, defined as resting supine heart rate >130 beats per minute, persisting for at least 10 minutes.
- Two participants per cohort who receive ATH-399A exhibit symptomatic bradycardia, defined as heart rate <40 beats per minute, or asymptomatic bradycardia, defined as resting supine heart rate <30 beats per minute while awake, persisting for at least 10 minutes, or clinically significant arrhythmia.
- One participant per cohort who receives ATH-399A exhibits abnormal liver tests defined as:
 - Aspartate aminotransferase (AST) or alanine aminotransferase (ALT) $>5X$ upper limit of normal (ULN).

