 - AST or ALT $>3X$ ULN along with one of the following criteria:
 - sustained for more than 2 weeks or
 - total bilirubin level $>2X$ ULN or
 - international normalized ratio (INR) time $>1.5X$ ULN or
 - the appearance of fatigue, nausea, vomiting, right upper abdominal pain or tenderness, fever, rash, and/or eosinophilia ($>5\%$).
 - Alkaline phosphatase (ALP) $>3X$ ULN.
 - ALP $>2.5X$ ULN and total bilirubin $>2X$ ULN.

- ALP >2.5X ULN with the appearance of fatigue, nausea, vomiting, right upper abdominal pain or tenderness, fever, rash, and/or eosinophilia (>5%).
- One participant per cohort who reaches a plasma AUC₀₋₂₄ of $\geq 1,800 \text{ h}^*\text{ng/mL}$.
- Two participants per cohort who receive ATH-399A exhibit renal toxicity, defined as serum creatinine $\geq 1.5X \text{ ULN}$ (confirmed by repeating within 24 hours).
- Two participants per cohort who receive ATH-399A exhibit hematologic toxicity, defined as one or more of the following (confirmed by repeating within 24 hours):
 - Leukocyte count $<2.5 \times 10^9/\text{L}$
 - Neutrophils $< 1.3 \times 10^9/\text{L}$ and $< 1.0 \times 10^9/\text{L}$ for Afro-American participants
 - Platelet count $<75 \times 10^9/\text{L}$

In addition, the SRC may stop dose escalation or descend to a dose level lower than the planned next higher dose level at any time if the SRC determines that dose escalation would pose undue risk to participants. If dose escalation is not stopped, the SRC may recommend ascending to the planned next higher dose level cohort, ascending to a dose level lower than the planned next higher dose level, or may repeat dosing at the current dose level.

Initially, for Parts 1a and 2, the safety and any available PK data will be reviewed by the SRC in a blinded manner (e.g., without participant identifiers or using reblinded participant numbers), but if the SRC considers it necessary due to a safety concern, individual participant data or an entire cohort's data may be unblinded to the SRC to enable decision-making. Before any such unblinding, the reason for unblinding should be documented.

Unblinding to validate treatment group where stopping criteria is met will be determined by SRC members. Subsequent dose escalation or descent will depend on if stopping criteria was met by participants who received ATH-399A as opposed to placebo.

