13.1.5 Committees Structure

13.1.5.1 Safety Review Committee

An SRC will be established to review safety and any available PK data and to oversee the overall conduct of the study with the primary purpose of protecting the safety of participants participating in the study. Details concerning the specific objectives, roles, responsibilities, and data review procedures of the SRC are documented in a separate SRC Charter document. The SRC will be composed of at least the Investigator, one medically qualified Sponsor representative and an independent MM.

The SRC may consult with or add members that include, but are not limited to, physician(s) scientists, biostatisticians, or other subject matter experts.

The SRC will meet as soon as is feasible, upon the occurrence of safety signals and after completion of dosing a given cohort to recommend acceptability of continued dosing, as well as escalation, de-escalation, or whether to add additional participants at the current dose level.

All data (reports) that are provided and reviewed by the SRC, including any minutes and decisions from the meetings, will be archived. The minutes will document clearly any questions posed and decisions reached and whether these decisions were unanimous.

SRC meetings will be held after safety and tolerability data up to at least 48 hours post-dose (Day 3) are available for at least 6 evaluable dosed participants from a same cohort for the SAD part, and after safety and tolerability data up to at least 24 hours post-last dose (Day 12) are available for all dosed evaluable participants from a same cohort for the MAD part. PK data up to 24 hours post-dose (post-last dose for the MAD part) will also be reviewed to evaluate if PK parameters in humans are as anticipated. The SRC will consider the data on a cohort basis, but also on the basis of cumulative information across cohorts as the study progresses.

The potential decisions of the SRC are:

- Escalate to the next planned dose level;
- Continue the study with a more conservative approach, such as decreasing to a dose-level lower than the planned next higher dose level, descending from a higher dose level to a lower dose level, repeating a dose level, or exploring an alternative dosing regimen in the MAD part (not exceeding the total daily dose planned in the protocol for that given cohort);

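### On the scheduled Part 1a labs and the Section 7.3 data cut, the two-week AST/ALT limb cannot be shown when escalation is decided; it depends on unscheduled repeats and an optional SRC hold

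*Protocol*

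**What the plan says.** The Synopsis and Section 7.3 of the Protocol give one list of criteria on which the SRC must stop escalation or choose a dose below the planned next level. The list makes no distinction between Parts 1a and 2. One liver criterion, met by a single ATH-399A recipient, is AST or ALT above 3X ULN plus one of four qualifiers. The first reads "sustained for more than 2 weeks or" and leads on to raised bilirubin, raised INR, and symptoms or eosinophilia.

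**Part 1a timing.** Table 1, footnote 7, schedules post-dose chemistry on "Day 1 at 8 hours post-dose (in not-fasted state), at Day 2 (in fasted state), at Day 3 (in fasted state), and at Follow-up". Footnote 1 adds: "Follow-up examination will take place on Day 8 (or between Day 8 and 11". Under Section 7.1.1, after each dose level "an SRC will review the safety and tolerability data through the follow-up visit of a minimum of 6 evaluable participants". Section 7.3 likewise requires "Safety/tolerability data through the final follow-up visit for each of the 6 evaluable participants in a cohort" before ascending.

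**Part 2 timing.** Table 3, footnote 7, schedules post-dose chemistry "on Day 1 at 8 hours post-dose (in not fasted state) and on Days 2, 6, 13 (in fasted state), and Follow-up (in fasted state", with Follow-up on Day 19 to 22. Section 7.1.3 puts first dosing of Cohort 2 about 3.5 weeks after first dosing of Cohort 1.

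**A second data cut.** Section 13.1.5.1 states, for the SAD part, that "SRC meetings will be held after safety and tolerability data up to at least 48 hours post-dose (Day 3) are available" (the minimum number of evaluable participants is 6). For the MAD part it asks for data to 24 hours after the last dose.

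**Related provisions.** Section 11.6.5 calls for clinically significant abnormal labs to be repeated until they normalise or lose significance. Section 13.1.5.1 lets the SRC suspend escalation while it determines whether a stopping rule has been met, and has it consider data cumulatively across cohorts. Section 7.3 lets it stop at any time for undue risk.

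**The concern.** A criterion defined by duration can act on a decision only if the observation before that decision is longer than the duration. In Part 1a the scheduled observation is shorter.

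Take a participant with ALT at 4X ULN on Day 3 and again on Day 11, with no symptoms and no rise in bilirubin, INR or eosinophils. On scheduled data this person meets no listed liver criterion when the SRC reviews the cohort, and has no further scheduled visit. No sentence says how the SRC should count the value.

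This is a first-in-human escalation, and the limb is mandatory. If it can be shown only when someone chooses to repeat a test and the SRC chooses to wait, the escalation relies on discretion where the plan states a rule.

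**Working it through.** **Check of the calendar convention.** With no Day 0, Day -1 plus Days 1 to 8 is 1 + 8 = 9 days. This matches the approximately 9 days on study that the Synopsis gives for Part 1a.

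**Formula.** Scheduled span = Follow-up day minus the day of the first post-dose sample above 3X ULN. The limb needs a span of more than 14 days.

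**Part 1a (Follow-up on Day 8 to 11)**

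| First seen | Span to Day 8 | Span to Day 11 | More than 14? | First day past 14 days |
|---|---|---|---|---|
| Day 1 (8 h) | 7 − 8/24 = 6.7 | 10 − 8/24 = 9.7 | No | Day 16 |
| Day 2 | 6 | 9 | No | Day 17 |
| Day 3 | 5 | 8 | No | Day 18 |

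Days 16 to 18 fall 5 to 7 days after the latest Follow-up day. A rise first seen at a Day 8 Follow-up would pass 14 days on Day 23. The exclusion of anyone above 1.2X ULN at screening or Day -1 means the rise should not predate dosing; even counting from Day -1 to Day 11 gives only 1 + 10 = 11 days. Five cohorts give four planned escalation steps, and the result is the same at each.

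**Part 2 (Follow-up on Day 19 to 22)**

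| First seen | Span | Can scheduled labs show it? |
|---|---|---|
| Day 1 (8 h) | 17.7 to 20.7 | Yes |
| Day 2 | 17 to 20 | Yes |
| Day 6 | 13 to 16 | Only if Follow-up is on Day 21 (15) or Day 22 (16) |
| Day 13 | 6 to 9 | No |

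A rise first seen on Day 13, after all 12 doses, reaches 14 days on Day 13 + 14 = Day 27 and exceeds it on Day 28, which is 27 days (27/7 = 3.9 weeks) after first dosing. Cohort 2 is planned at about 3.5 × 7 = 24.5 days after first dosing, so around Day 25 to 26. Even complete unscheduled follow-up could not show this case before that planned start.

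**Under the Section 13.1.5.1 cut.** Part 1a data to Day 3 span at most 2 − 8/24 = 1.7 days. Part 2 data to 24 hours after the last dose (Day 13) span at most 13 − 1 = 12 days. On this cut, scheduled labs cannot show the limb in either part.

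**Share of the liver criterion affected.** There are eight limbs: AST/ALT above 5X ULN; above 3X ULN with each of four qualifiers; and three ALP limbs. One of the eight depends on two weeks of observation.

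**The case against.** A reader might infer that the criterion cannot be met in Part 1a at all and that this safeguard does not function. The documents do not support that.

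- The limb does not say that only scheduled labs count. Section 11.6.5 repeats have no Day 11 limit, and Section 11 allows unscheduled safety samples.
- Data through Follow-up are the minimum for a decision, not a deadline. No interval between Part 1a cohorts is given.
- The suspension option in Section 13.1.5.1 fits a pending persistence criterion. Cumulative review can bring a late result to a later decision, and escalation needs the members' mutual agreement.
- In Part 2, with repeats, a rise first seen on Day 6 passes 14 days after Day 20, before Cohort 2 is due.

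All of this stands, and it limits the claim to scheduled data and the stated cut. It does not remove the gap. The repeats depend on a judgement of clinical significance and have no stated interval. Suspension is one of several possible decisions, not a required response. A late result may arrive after the next cohort has been dosed. The SRC Charter, which may cover pending labs, is not among the documents reviewed.

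A reader might also take the absence of the two-week limb from the Section 10.1 list as an error. That list governs review of sentinel data before the rest of the cohort is dosed, nominally after 48 hours under the Protocol. A two-week criterion has no use there, so leaving it out is logical.

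**Conclusion.** The point holds in limited form. On scheduled Part 1a labs and the Section 7.3 cut, a mandatory liver limb cannot be shown at any of the four planned escalation decisions: at most about 10 days are observed against more than 14. In Part 2 it can be shown for early rises but not for one first seen after the full 12 doses, where the planned Cohort 2 start comes before two weeks have passed.

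This assumes that duration runs from the first sample above 3X ULN, that the SRC decides on data through Follow-up without waiting, and that the approximately 3.5-week interval is kept. How often the SRC would in practice meet before Day 16 to 18 in Part 1a cannot be computed, because no cohort interval is stated.

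The result does not show that the liver safeguards fail as a whole, since the other seven limbs need no two-week observation. It shows one rule that rests on discretion, together with two SRC data cuts that disagree. It is worth correcting because it bears on participant safety.

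**What to change.** 1. Reconcile the two-week wording in the Synopsis and Section 7.3 with Follow-up on Day 8 to 11 (Part 1a) and Day 19 to 22 (Part 2), and with the approximately 3.5-week interval between Part 2 cohorts.
2. Reconcile the SRC data cuts: Section 7.3 runs through Follow-up, while Section 13.1.5.1 stops at Day 3 for SAD and 24 hours after the last dose for MAD.
3. State in Section 7.3 how a value still above 3X ULN at the last scheduled visit counts for the SRC decision, linking the Section 11.6.5 repeats to the suspension option in Section 13.1.5.1.
4. Leave the Section 10.1 sentinel list unchanged.

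The persistence period or waiting rule is for the sponsor and the SRC to decide; none is proposed here.

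Cost: wording in the Synopsis and Sections 7.3 and 13.1.5.1, with no new routine procedure. Escalation could be delayed, but only in a cohort with an unresolved transaminase rise.
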